Pregnancy test	x	x*							
Low Energy Availability in Females Questionnaire	x								
Vitamin D Questionnaire	x								
Blood via venipuncture									
CBC	x								
TSH	x								
Progesterone		x							
Vitamin D (total and free 25(OH)D)		x							

22-168 The Effect of Impact Loading on Bone Biomarkers in Energy-Restricted Female Runners

N-terminal propeptide of type 1 procollagen		x						x
Undercarboxylated osteocalcin		x						x
Sclerostin		x						x
C-terminal telopeptide of type 1 collagen		x						x
Parathyroid hormone		x						x
Estradiol		x						x
Insulin-like growth factor-1		x						x
Hepcidin		x						x
Markers of iron status (Ferritin, iron, total iron-binding capacity [TIBC])		x						x
Insulin		x						x
Thyroid hormones (Free triiodothyronine (T3), free thyroxine and rT3)		x						x
Leptin		x						x
Cortisol		x						x
Nesfatin-1		x						x
Health outcomes								
Continuous glucose monitoring			x	x	x	x	x	
Compliance and Fitness Testing								
Habitual dietary intake (food records for 3 days)	x							
Habitual exercise tracking (smart watch for 3 days)	x							
Running Economy			x				x	
Aerobic Capacity (VO ₂ max)	x							
Treadmill running at 65% VO ₂ max			x	x	x	x	x	
Physical Activity tracking (smart watch)			x	x	x	x	x	
Mealtime Log			x	x	x	x	x	

Note: The 5-day intervention, RUN or RUN+IL, occurs on days 2-6

**pregnancy test performed at only 2 timepoints: baseline and day 1 of the second experimental condition after the 3-week washout period*

8.2 Provide a description of:

- All research procedures being performed
- If the study has more than one procedure, session, and/or subject population, describe each procedure, session, and/or study

population separately. For complex studies, you are encouraged to include a figure or chart.

Phone Screen

Those who respond to the investigator's advertisements will be scheduled to complete a brief telephone (or HIPAA-compliant Zoom) screening to confirm basic eligibility criteria. Participants will be made fully aware of the eligibility criteria, time commitment, possible risks and their right to withdraw from the study at any time. A phone screening script and phone screening data collection form will be used for phone screening conducted by a registered dietitian nutritionist.

Baseline Screening (approximately 1 hour)

Informed Consent: Participants will be provided an informed consent form following the phone screening and in advance of coming to the laboratory.

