Health History: Subjects will be asked to complete a standard health/medical history questionnaire, which will be used to screen for health issues (e.g., coronary or congenital heart disease) or other reasons (medications which influence study results) that would preclude participation (see uploaded Health History Screening Questionnaire). This questionnaire has been used by [name] for clinical studies for the past 17 years.

Low Energy Availability in Females Questionnaire (LEAF-Q): Subjects will be asked to complete the LEAF-Q, which will be used to screen for risk of existing LEA, medication use, menstrual function, and injury history. The LEAF-Q has been validated as a screening tool for LEA in female endurance athletes (Melin, Tornberg et al. 2014). Individuals who score as "high risk" for LEA will be provided referral information to a local sports dietitian.

Body Weight Height and Composition: Body weight and height will be measured on a digital physician's scale. Percent body fat and fat-free mass will be measured in all subjects via DXA scan.

Bone Mineral Density: Total body, dual-femur, and lumbar spine BMD will be measured in all subjects via DXA scan. Scans will be conducted by [name] who is an ISCD Certified Bone Density Technologist.

Urine sample and pregnancy test: All participants will be required to provide a small cup of urine immediately before the DXA at baseline. The urine will be evaluated for hydration status via specific density using a refractometer. A pregnancy test will be performed on the urine sample for all participants.

Baseline Laboratory Testing Session (approximately 1 hour).

22-168 The Effect of Impact Loading on Bone Biomarkers in Energy-Restricted Female Runners

All measurements will be performed in the morning after a 12-hour fast (no caffeine) with the participants instructed not to engage in heavy exercise for 36 hours prior to testing and to adequately hydrate the evening prior.

Blood Draw: Blood will be drawn by venipuncture after a 12-hr fast (no caffeine) for the following: CBC, TSH, and progesterone. In total, blood will be drawn five times during the study by venipuncture from a vein in the arm. These include baseline, and the days immediately before and after each experimental condition as explained below. Blood will be drawn with the participant seated quietly in a phlebotomy chair. Approximately 10 ml will be obtained during the baseline visit.

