22-168 The Effect of Impact Loading on Bone Biomarkers in Energy-Restricted Female Runners

body weight will be measured on a digital physician's scale. Participants will complete the LEA experimental trials on days 2-6. A follow-up blood sample will be collected on the morning of day 7 after an overnight fast and body weight will be measured on a digital physician's scale.

Pregnancy Test: a pregnancy test will be performed after the 3-week washout period on day 1 of the second experimental condition.

Blood Draw: Blood (approximately 20-25 ml) will be drawn the days before and after each LEA experimental trial by venipuncture after a 12-hr fast (no caffeine) for the following: Progesterone, total and free 25(OH)D, N-terminal propeptide of type 1 procollagen, undercarboxylated osteocalcin, sclerostin, C-terminal telopeptide of type 1 collagen, parathyroid hormone, estradiol, insulin-like growth factor, hepcidin, ferritin, TIBC, iron, cortisol, leptin, nesfatin-1, insulin, free T3, free T4, rT3. In total, blood will be drawn five times during the study by venipuncture from a vein in the arm with a total of 110 ml obtained for the duration of the study. Blood will be drawn with the participant seated quietly in a phlebotomy chair.

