Eligible participants will be well-trained, eumenorrheic female runners between the ages of 18-35 years that are weight-stable with a BMI between 18.5-30 kg/m². Participants with LEAF-Q scores ≥ 8 , existing menstrual disturbances measured by progesterone and self-report, or low BMD (z-score <-2) will be excluded from the study to prevent worsening existing conditions and recommended to follow up with their primary care physician and/or a registered dietitian nutritionist. During the phone screening, participants will be asked if they have ever been diagnosed with an eating disorder and the circumstances surrounding the diagnosis. If the participant has just recently recovered (within the last 12 months) or is still in recovery, she will be excluded from the study. The LEAF-Q was not developed to assess disordered eating behavior, however, a study in ultra-marathon female runners found a significant association between high LEAF-Q scores and disordered eating (Folscher, Grant et al. 2015). Athletes who score 8 or higher on the LEAF-Q will be excluded from the study and referred to a local sports dietitian. Participants using contraceptives (oral contraceptives, injections, IUD, etc.) will be excluded from this study. Contraceptive use may mask menstrual irregularities and oral contraceptives may influence glucose metabolism (Lopez, Schultz 2007), a secondary outcome of this study. Adequate training status for the study protocol will be assessed based on running volume, frequency, and VO₂max. Eligible participants must be able to run on 5 days/week for at least 60 minutes to meet the training requirements of the study protocol. Additional exclusion criteria include history of fracture in previous 6 months, medication use that could potentially affect bone metabolism (e.g., corticosteroids, anticonvulsants, heparin, gonadotropin-releasing hormone agonists), pregnancy, lactation, abnormal TSH, and routine engagement in mechanical loading exercises. Participants must be willing to consume the diets provided, however, diets will be modified based on patient allergies or preferences, within reason. Participants will be excluded if they have dietary restrictions or preferences that would prevent them from consuming meals that fit within the experimental conditions. For example, we cannot modify diets to meet low-carbohydrate preferences given the experimental diets must contain 55% of total calories from carbohydrates. Similarly, participants who are unable to consume high-fiber diets will be excluded.

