
12.3 Indicate specifically whether you will include or exclude each of the following special populations: (You may not include members of these populations as subjects in your research unless you indicate them in the description of your subject population.)

- *Minors, as defined by state law where the study is performed (infants, children, teenagers)*
- *Pregnant women (can be included in minimal risk studies by mentioning in section 13.1)*
- *Prisoners (including all incarcerated individuals)*
- *Adults not capable to consent on their own behalf*

None of the above will participate.

Pregnant women are excluded because intentional energy restriction is not appropriate during pregnancy. A pregnancy test will be performed at baseline prior to the DXA scan and after the 3-week washout period on Day 1 of the second experimental condition.

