It is possible that participants could develop soreness in legs by participating in our high-volume running regimen on 5 consecutive days and during the 5-day intervention with high-impact jumping. It is also possible an unknown allergy to foods contained in the controlled diets could be identified during the study. These events, however, are not likely. To minimize the potential, we will only recruit participants with current long-distance running experience at a high volume (at least 30 miles per week) and frequency (at least 5 days per week) to meet the exercise demands of the protocol.

17.4 If applicable, indicate which procedures might have risks to an embryo or fetus should the subject be or become pregnant:

Dietary restriction is a risk to the development of the fetus should the subject become pregnant during the study intervention. Pregnancy tests will be performed at baseline testing (specifically before the DXA) and after the 3-week washout period on Day 1 of the second experimental condition, to ensure the participant is not pregnant. Progesterone will be measured to ensure menstrual status. Participation in the study would end if it were determined the participant has become pregnant.

17.5 If applicable, describe risks to others who are not subjects (e.g., collection of sensitive health data that might affect sexual partners if disclosed, mandatory reporting of abuse, DNA testing that might affect family members or relationships):

N/A

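### Condition 1 starts the restricted diet without a Day 1 pregnancy test, although condition 2 requires one under the same diet and the same menses-start rule

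*Combined protocol and SAP*

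**What the plan says.** The testing schedule is the same wherever it appears in the combined protocol and SAP.

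- **Section 8.1, Table 1 footnote:** "pregnancy test performed at only 2 timepoints: baseline and day 1 of the second experimental condition after the 3-week washout period".
- **Section 8.2, screening visit:** "All participants will be required to provide a small cup of urine immediately before the DXA at baseline". The pregnancy test is done on that sample, for every participant.
- **Section 8.2, intervention:** "a pregnancy test will be performed after the 3-week washout period on day 1 of the second experimental condition". Sections 12.3 and 17.4 repeat the same two occasions.

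The reason for testing is also clear. Section 12.3 says "Pregnant women are excluded because intentional energy restriction is not appropriate during pregnancy", and Section 17.4 says "Dietary restriction is a risk to the development of the fetus should the subject become pregnant during the study intervention".

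Three other provisions bear on the point.

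- **Menses-start rule (8.2):** both conditions are to begin on the second or third day of menstruation. Section 24.1 shows that the team learns of the bleed from the participant.
- **Progesterone:** the baseline draw in 8.2 is "for the following: CBC, TSH, and progesterone", and Table 1 also marks progesterone on Day 1 of each condition. Section 17.4 gives its purpose: "Progesterone will be measured to ensure menstrual status".
- **Contraception (12.2):** "Participants using contraceptives (oral contraceptives, injections, IUD, etc.) will be excluded from this study".

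**The concern.** The hazard is the diet, and the diet is the same in both conditions: 30 kcal/kgFFM/d on Days 2 to 6. The menses-start rule is also the same. Yet the plan adds a same-visit urine test only before the second exposure. If a reported period were enough, the condition 2 test would not be needed. If it is not enough, condition 1 lacks a check that condition 2 has.

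The earlier test does not fully fill that place. It is timed to the radiation exposure of the DXA and not to the diet, and nothing limits how old it may be when condition 1 starts. What is at stake is participant safety: a woman whom 12.3 would exclude could begin the restricted diet because a bleed that was not a true period was reported as one.

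**Working it through.** There is no power, alpha or sample-size figure to reproduce. The check sets the safeguards for the two conditions side by side, then asks what the documents allow one to say about the age of the screening test.

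**Safeguards before the Day 2 diet**

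| Safeguard | Condition 1 | Condition 2 |
|---|---|---|
| Screening urine test before DXA (8.2) | Yes, no maximum age | Yes, older still |
| Start on day 2 or 3 of menstruation (8.2) | Yes | Yes |
| Day 1 progesterone (Table 1) | Yes, no turnaround stated | Yes, no turnaround stated |
| Day 1 urine pregnancy test (Table 1 footnote, 8.2, 12.3, 17.4) | **No** | **Yes** |

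The last row is the only difference in kind. On progesterone, no section requires the result before Day 2, and 19.3 has blood samples stored frozen until analysis.

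**Age of the screening test at condition 1: lower end**

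Section 8.2 places the DXA and urine test at the screening visit, then the baseline laboratory session, then three days of diet and exercise tracking, then the conditions. With the three tracking days after testing, the test is at least a few days old on Day 1 of condition 1.

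**Age of the screening test at condition 1: upper end**

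Inputs: participation of approximately 6 to 10 weeks (11.1), that is 42 to 70 days; two conditions of 7 days (1.0), that is 14 days; a washout given as approximately 3 weeks (5.1, 11.1) or approximately 24 days (1.0, 8.1). Taking these at face value and putting all remaining time before condition 1:

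- At 6 weeks: 42 − 14 − 24 = 4 days, or 42 − 14 − 21 = 7 days.
- At 10 weeks: 70 − 14 − 24 = 32 days, or 70 − 14 − 21 = 35 days.
- If the 24 days run from the start of one condition to the start of the next, the two conditions span 24 + 7 = 31 days, leaving 42 − 31 = 11 to 70 − 31 = 39 days.

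These figures include the lead time from phone screen to screening visit. They also assume that none of the slack is taken up by a longer cycle between the conditions.

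**Why these are not bounds**

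Section 8.3 puts all five blood draws, from the baseline draw to the last Day 7, within 5 to 6 weeks. The same subtraction at 5 weeks gives 35 − 14 − 21 = 0 days and 35 − 14 − 24 = −3 days between the baseline draw and condition 1. A negative interval shows that the durations are too rounded for day-level arithmetic. At 6 weeks the result is at most 4 to 7 days, so a screening test several weeks old would need most of the gap to fall between the screening and baseline visits. No section describes such a gap, and none rules it out.

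The documents therefore support this and no more: at least a few days, possibly several weeks, with no stated limit.

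**The case against.** The strongest reply is that this is a deliberate, consistently stated choice and that condition 1 is already well protected. Every participant has a negative urine test at screening. Participants must be eumenorrheic (12.2) and start on day 2 or 3 of menstruation. A period after a negative test is strong evidence against pregnancy, so the age of the test overstates the risk. The retest is also better justified at condition 2, where the screening test would be about a full cycle older.

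Most of that stands, and it is why the point is minor. It does not explain why the plan adds a test to the menses rule in one condition and not in the other.

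Two further replies have partial force.

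- **Progesterone.** Its sentence sits in the answer on fetal risk in 17.4, so the plan does offer it as part of this safeguard. It remains a measure of menstrual status, and its result need not be known before the diet starts.
- **Contraception.** Excluding users removes their protection between screening and condition 1. It also removes contraceptive-induced bleeding as a source of false periods, which strengthens the menses rule. The exclusion cuts both ways.

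A reader might infer that the screening test would commonly be a month or more old, or that screening is booked without regard to the cycle. The documents support neither. The long intervals come from loading every spare day before condition 1, and the text is silent on how screening is timed to the cycle. The amendment log notes that a menstrual cycle question was added to the phone screening form.

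**Conclusion.** The point holds as a low-severity safety gap with a cheap remedy. The first exposure to a diet that the plan itself calls a fetal risk is preceded by a urine test of unlimited age, a participant-reported bleed and a progesterone result that may not yet be known. The second exposure has a Day 1 urine test as well.

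The likely size is small. What remains is mainly a reported bleed that is not a true period, in a woman who was negative at screening. The documents give no rate for this, so no probability is offered. The conclusion assumes that the order of visits in 8.2 is followed and that no screening-to-condition-1 limit exists in forms not included here.

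A reader might also infer that the protocol contradicts itself or that the trial's results are at risk. Neither follows: the two-test schedule is stated consistently, and the analysis and sample size do not depend on it.

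**What to change.** Perform the existing urine test on Day 1 of both conditions and read it before the Day 2 diet starts. The Table 1 footnote could read: *pregnancy test performed at 3 timepoints: baseline (before DXA) and Day 1 of each experimental condition*. Sections 8.2, 12.3 and 17.4 should be changed to match.

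A weaker alternative is to state a maximum interval from the screening test to Day 1 of condition 1 and retest if it is exceeded. The investigator would have to choose that limit, since the documents do not supply one.

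The cost of the main fix is wording in four places and one more urine strip per woman, three instead of two, so at most about 20 more given the enrolment target of 20 in Section 14.1. The Day 1 visit already takes place, so no visit or blood draw is added.

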9.0 Data and Specimen Long Term Storage and Use

9.1 If you will store data or specimens for future use, describe where you will store the data or specimens, how long they will be stored, and how and by whom the data or specimens will be accessed:

All data will be stored in a locked cabinet in [name] laboratory which will also be locked to only authorized personnel. The computer data will be stored in the

22-168 The Effect of Impact Loading on Bone Biomarkers in Energy-Restricted Female Runners

locked lab on a computer that is password protected. All de-identified data will be kept indefinitely.

9.2 For specimens, list the data to be stored or associated with each specimen:

Blood and urine samples will be stored in a -80-degree freezer in the HIP laboratory currently located in the Garvin Building. Samples will be labeled with the participants' study code (see section 9.4 below), the visit number and the date and time of the collection. No identifying information will be written on specimen samples. The freezer is located in locked room/laboratory.

Blood analyzed by the Metabolic Core at Virginia Tech, housed in the Integrated Life Sciences Building, may also be temporarily stored in a freezer in this laboratory immediately before, during or after analysis.

9.3 Describe the procedures to release data or specimens outside of the research team, including the process to request a release, approvals required for release, who can obtain data or specimens, and what data will be provided with specimens:

Some de-identified blood and urine samples will be sent to a commercial laboratory for analysis based on cost savings. There are currently no plans to release data outside of the research team.

9.4 Describe the identifiers to be included with stored data or specimens, as well as any key or code that could be used to make them identifiable. Describe where the code will be stored, who will have access to it, and when it will be destroyed:

Study Codes using a combination of letters and numbers will be used to de-identify subjects from their personal information. No obvious identifiers will be stored with the data; the data spreadsheet, however will include each participants' age and starting weight as part of the de-identified data. Original de-identified data collection sheets will be stored in a locked file cabinet as part of study records; scans of some de-identified information may be kept in a password-protected electronic file that is accessible only to research personnel. During the active phase of the study, a master document (key) that will contain the participants name, assigned study code and randomization order will be kept in a password-secured file that will be accessible only to the PI and authorized study personnel (doctoral student in charge of the study, [name]). The key will be destroyed 6 to 12 months after collection of data from the last participant. De-identified data may be kept indefinitely. Blood and urine samples will be destroyed after 5 years.

9.5 *Please select the identifiers you will obtain (whether directly from participants or from another source), including but not limited to:*

	Name
	Geographical subdivisions smaller than a state, including street address, city, county, precinct, zip code, and equivalent geocodes (note, the initial three digits of a zip code are not considered identifiable)
	Elements of dates (except year) for dates directly related to an individual, including birth date, admission date, discharge date, date of death, and single year of age over 89 and all elements of dates (including year) indicative of such age (note, such ages and elements may be aggregated into a single category of age 90+)
	Phone numbers
	Fax numbers
	Electronic mail addresses (e-mail)
	Social Security numbers
	Medical record numbers
	Health plan beneficiary numbers
	Account numbers
	Certificate/license numbers
	Vehicle identifiers and serial numbers, including license plate numbers
	Device identifiers and serial numbers
	Web Universal Resource Locators (URLs)
	Internet protocol (IP) address numbers
	Biometric identifiers, including finger and voice prints (audio recording)
	Full face photographic images and any comparable images (including video recording)
	Student record number or identification number
	User name for online or computer accounts
	Any other unique identifying number, characteristic, or code (note this does not mean the unique code assigned by the investigator to code the data): Click here to explain.

